**Study design.** We will conduct a two-arm, parallel randomised controlled trial (RCT) to evaluate the effects of the MB programme. Randomisation involving computer-generated two-digit random numbers (even and odd) (Excel 2007, Microsoft, Redmond, WA, USA) will be used to allocate participants in sequence to either the intervention group or control group in a 1:1 ratio after they have provided consent to participate. The allocation will be blinded to the participants and the data analyst. The random allocation will be conducted by a research assistant who will not be involved in the intervention and data analysis. Participants in the experimental arm will receive a 6-week MB programme. Participants in the control arm will receive a 6-week placebo control programme and will be blinded to the study details. Data will be collected from both groups at three time points: before-intervention (T0), after-intervention (week 6; T1) and 1-month follow-up (week 10; T2), except the salivary cortisol levels which will be assessed at T0 and T1. Figure 2 depicts the flow of the study.

**Subject recruitment.** The participants will be recruited from universities and district

centres through emails, social media, leaflets and posters. Inclusion criteria: young people (aged 18 to 30); moderate level of stress (Perceived Stress Scale (PSS-10) score  $\geq 14-26/40$ ); a liking for music. Exclusion criteria: participants diagnosed with an acute mental problem; participants under the influence of drugs that affect the nervous system; having previous experience with imagery evoked by music and meditations where music is played.

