**Experimental group.** The experimental group will receive the MB programme in 6 weekly sessions (each session lasts 2 hrs in a group of 6 participants) delivered in a confined and quiet room on the campus, plus a session of home practice on a weekly basis. The study intervention will be delivered by a certified music therapist who has been trained by the Co-I, [name]. At the beginning of the first session, information on the concept of mindfulness will be delivered. The MB will comprise three components, including therapist-guided meditative breathing, breathing with music listening, drawing a mental image of the breathing practice with a circle as a reference and sharing and processing of the experience ([name], 2019). The detail of the study intervention is presented in Table 1. **Home practice** will be carried out according to a weekly schedule during the 6-week intervention; the participants will record the frequency and duration of home practice: mindful breathing, music listening and drawing images. In the orientation during the first week, the participants will be asked to work out a plan for implementing home practice and to complete an online schedule during the subsequent weeks. To increase the compliance rate, they will also receive reminders to perform their home practice via WhatsApp messages or email. The research team will monitor the participants' progress, provide motivation and encouragement to continue the home practice.

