**Control group.**

Participants (6-8 participants per group) will receive a 30-minute Mental Health Education Programme (MHE) in the first meeting (week 1) and second meeting (week 6). The content of the MHE is adopted from the Student Health Service, Department of Health, HKSAR. The MHE is comprised of the following topics:

What is Stress?

[https://www.studenthealth.gov.hk/english/health/health\\_ph/health\\_ph\\_stress.html](https://www.studenthealth.gov.hk/english/health/health_ph/health_ph_stress.html));

Tips on Being Joyful

<https://www.chp.gov.hk/archive/joyful/en/contentsab5e.html?id=40>);

Breathing Exercise practice

[https://www.studenthealth.gov.hk/english/emotional\\_health\\_tips/eh\\_tips/eh\\_tips.html](https://www.studenthealth.gov.hk/english/emotional_health_tips/eh_tips/eh_tips.html));

and

Music listening.

A take home kit which consists of the fact sheet information of the health talk and the video link of the breathing exercise and musical pieces will be provided to the participants after the first meeting. They are instructed to practice the breathing exercise and listening to the musical pieces at home. A weekly reminder via WhatsApp message and email will be sent to the participants to enhance their compliance. In the second meeting, participants will receive the revision talk about on the MHE and share their experience in stress management with the group members.

**Treatment Fidelity.** To ensure treatment fidelity, the certified music therapist will have at least 25 hours of MB programme training; the implementation of the intervention will be supervised by [name], the Co-I. The group sessions will be audio-taped with the consent of the participants, and the recordings will be given to the supervisor for quality monitoring. Written session reports will be provided and regular meetings via Zoom (i.e., three supervisions in the first group, and then two supervisions in the subsequent groups) will be arranged for maintaining the quality of the intervention. The research team will discuss any issues that may arise regarding the study protocol to ensure the quality and consistency of study intervention via regular face-to-face or online meetings.

**Measures.** Primary and secondary measures will be collected at before-intervention (T0), after-intervention (week 6; T1) and 1-month follow-up (week 10, T2) via a self-administered questionnaire. The salivary cortisol levels will be collected at T1.

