**Statistical analysis.** The statistical analysis will be performed in accordance with the study design, RCT with an intention-to-treat analysis using SPSS, Version 26. The baseline characteristics of the participants in the two arms will be compared to identify any clinically meaningful differences at baseline and at each time point using Chi-square test (for nominal data), Mann-Witney U test (for ordinal or non-normality data) or t-test (for normality data). Any variables considered to be significantly different will be further evaluated (e.g., included as covariates in the statistical analyses) and adjusted to account for their potential confounding effects on the outcomes. To measure both the primary and secondary outcomes, we will obtain repeated measures of multiple outcomes in the two groups, and the data will be analysed using a multivariate approach, such as a MANCOVA or Generalized Estimating Equation (GEE), with adjustment of the baseline outcome variables to test for between-group differences. Correlation analyses will be performed to determine the relationships among the dependent variables. Regression analyses and ANOVA will be conducted to assess significant differences in the effects of the demographic variables on each outcome variable. Repeated measures of ANOVA will be performed to explore the levels of sCort differing within subjects and between groups; between the two sampling days (day) and across the five sampling times (time). Path analyses will be conducted to test the mediating effects between stress-related symptoms and personal strength and emotional regulation. Sub-group analyses will be conducted according to categorisations such as

gender, coping style and religion.

**Ethical considerations.** Ethical clearance will be sought prior to the study from the study institution. Consent will be obtained and anonymity ensured to protect privacy. Participants will receive study information and have autonomy to withdraw from the study at any time.

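### Both arms are delivered in small groups, yet no planned analysis accounts for delivery group; any within-group correlation would push type I error above 5%, by an amount that depends on an unstated ICC

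*Combined protocol and SAP*

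**What the plan says.** All references are to the combined protocol and SAP.

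- **Study design:** a computer-generated sequence is used to "allocate participants in sequence to either the intervention group or control group in a 1:1 ratio". The unit of randomisation is the person.
- **Experimental group:** MB consists of "6 weekly sessions (each session lasts 2 hrs in a group of 6 participants". Its components include "sharing and processing of the experience", and Table 1 lists sharing in every session.
- **Control group:** "Participants (6-8 participants per group) will receive a 30-minute Mental Health Education Programme (MHE" at week 1 and again at week 6. At the second meeting members also "share their experience in stress management with the group members".
- **Sample size:** the only correlation given is 0.5 between repeated measures, which is within a person. There is no ICC for delivery group and no design effect.
- **Statistical analysis:** for the primary and secondary outcomes, "the data will be analysed using a multivariate approach, such as a MANCOVA or Generalized Estimating Equation (GEE". The section also lists correlation, regression, ANOVA, path and subgroup analyses. The outcome models are specified "with adjustment of the baseline outcome variables to test for between-group differences", where the groups compared are the trial arms. The section mentions no delivery group, random effect, ICC or cluster unit.

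**The concern.** After individual randomisation, participants in both arms are nested in small groups whose members interact. People who attend the same sessions may come to resemble one another through peer influence, the tone of the group or the way a session ran. Randomisation protects against biased assignment, but it does not remove correlation that arises afterwards.

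MANCOVA takes participants as independent. GEE allows for correlation only inside the cluster it is told about; the plan brings it in for repeated measures, so the natural reading is that the cluster is the person. Either way, positive correlation within delivery groups would leave the standard error of the arm difference too small and the true error rate above the stated two-sided 5%. This applies to every between-arm comparison, the primary outcome included.

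The arms also differ in exposure: 6 × 2 h = 12 hours of group contact in MB against 2 × 30 min = 1 hour in control. Any correlation may therefore be larger in MB, and a single common variance may not fit.

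**Working it through.** **Inputs from the documents.** Two-sided alpha 5%, power 90%, f = 0.25, three measurements, 232 evaluable (116 per arm), 20% attrition and 145 enrolled per arm (Sample size); MB groups of 6 (Experimental group); control groups of 6–8, midpoint 7 used (Control group).

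**Assumed.** ICC of the baseline-adjusted outcome 0.01 / 0.02 / 0.05 / 0.10, because the documents give none. Attrition is spread evenly, so 6 × 0.8 = 4.8 MB and 7 × 0.8 = 5.6 control participants are analysed per group.

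**Step 1. Reproduce the plan's figure.** A two-group MANOVA with three responses has noncentrality λ = N × f² = 232 × 0.0625 = 14.5 on F(3, 228), which gives 90.2% power. Then 116 / 0.8 = 145. Both stated figures are recovered, with participants taken as independent.

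**Step 2. Design effect.** For each arm, DE = 1 + (m − 1) × ICC, averaged over the two equal arms. In the MB-only case the control DE is 1. Example, MB only, ICC 0.05: MB DE = 1 + 3.8 × 0.05 = 1.19; average (1.19 + 1) / 2 = 1.095.

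**Step 3. Actual type I error.** For a single-contrast test that ignores groups, α = 2 × [1 − Φ(1.96 / √DE)]. In the example, 1.96 / √1.095 = 1.873, so α = 6.1%.

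| Scenario | | ICC 0.01 | 0.02 | 0.05 | 0.10 |
|---|---|---|---|---|---|
| MB only, thinned groups (4.8) | DE | 1.019 | 1.038 | 1.095 | 1.190 |
| | α | 5.2% | 5.4% | 6.1% | 7.2% |
| Both arms, thinned (4.8 / 5.6) | DE | 1.042 | 1.084 | 1.210 | 1.420 |
| | α | 5.5% | 6.0% | 7.5% | 10.0% |
| MB only, full groups (6) | DE | 1.025 | 1.050 | 1.125 | 1.250 |
| | α | 5.3% | 5.6% | 6.5% | 8.0% |
| Both arms, full (6 / 7) | DE | 1.055 | 1.110 | 1.275 | 1.550 |
| | α | 5.6% | 6.3% | 8.3% | 11.5% |

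**Step 4. Simulation check.** A one-time-point baseline-adjusted ANCOVA ignoring groups was run 40,000 times per setting, with 145 per arm, a random 116 retained and baseline correlation 0.5. It rejected 5.0% at ICC 0. At the four ICCs it rejected 5.2% / 5.4% / 6.0% / 7.4% (MB only) and 5.8% / 6.1% / 7.6% / 10.0% (both arms), in line with the formula.

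**Step 5. Power at 232 evaluable, thinned groups, once clustering is allowed for.** Replace λ by λ / DE. This is approximate and slightly favourable, since it keeps the participant-level denominator degrees of freedom.

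- Three-response MANOVA (90.2% at ICC 0): about 90% / 89% / 87% / 84% (MB only) and 89% / 87.5% / 83% / 76% (both arms).
- Repeated-measures between-arm test using the stated 0.5: λ = 232 × 0.0625 × 3 / (1 + 2 × 0.5) = 21.75, which gives 99.6% at ICC 0. The lowest value is at ICC 0.10 in both arms: 21.75 / 1.42 = 15.3, or 97.4%.

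**The case against.** The strongest reply is that the harm rests wholly on an ICC that no part of the document supplies. The protocol speaks of a certified music therapist in the singular, with a fixed session plan, audio-taping and supervision. If one therapist leads every MB group, variation between therapists disappears and the low end of the range becomes more plausible. This stands, although peer effects would remain and group sharing is part of the treatment.

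Control contact is also slight. Members meet for an hour in all, and sharing among them is described only at the week 6 meeting, the same week as T1. Equal clustering in both arms is therefore an upper case. A reader might take 11.5% as the expected error rate. The documents do not support that: the figure needs ICC 0.10, equal clustering in both arms and no thinning of groups.

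A reader might also infer that the trial is underpowered and must enrol more. That does not follow. The power loss depends on which test lay behind 232, and on the repeated-measures basis power stays above 97% throughout.

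Nor does the plan lay down a wrong analysis. Its wording is open, and a GEE clustered on delivery group is not excluded. The gap is in specification.

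Two limits on the figures also stand. They apply to a single contrast; a multi-response MANCOVA would inflate by a different amount, not computed here. They also assume even attrition; if whole groups left, the full-group rows would apply.

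**Conclusion.** The point holds, with modest and conditional size. It is certain that both programmes are delivered in groups and that no planned analysis accounts for this. How much it matters is not known. With clustering confined to MB and groups thinned by 20% attrition, the excess over 5% is 0.2 to 2.2 percentage points across ICC 0.01 to 0.10; with equal clustering in both arms it is 0.5 to 5.0 points. At ICC 0 there is none.

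Type I error is the main concern and power the lesser one. This is a cheap improvement worth making before analysis, and minor if the ICC is 0.02 or below.

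**What to change.** 1. **Data.** Record a delivery-group identifier in both arms. Include the assigned group for randomised participants who never attend, so that the intention-to-treat set can be analysed. Existing records should not be relied on for this: Treatment Fidelity says "Written session reports will be provided and regular meetings via Zoom", but not that the reports list who attended, and it describes no such reports for control.
2. **Analysis.** Name one of the following in the Statistical analysis section:
   - a linear mixed model with T1 and T2 as responses, T0 as covariate, and random effects for participant and delivery group, the delivery-group variance being allowed to differ by arm and to be zero in control, with Satterthwaite degrees of freedom; or
   - a GEE with delivery group stated as the cluster, robust standard errors and a small-sample correction. At 145 per arm there would be about 145 / 6 + 145 / 7 = 24.2 + 20.7, or roughly 45 clusters.
3. **Sample size.** State power at the planned N over an assumed ICC range, for clustering in MB only and in both arms.

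**Cost.** One data field, some analysis wording and a restated power; no extra enrolment is proposed. The stated power may fall below 90%. Confidence intervals widen by √DE − 1: with thinned groups about 1% / 2% / 5% / 9% (MB only) or 2% / 4% / 10% / 19% (both arms) at ICC 0.01 / 0.02 / 0.05 / 0.10. That widening reflects uncertainty that an analysis ignoring groups would leave out.

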**Control group.**

Participants (6-8 participants per group) will receive a 30-minute Mental Health Education Programme (MHE) in the first meeting (week 1) and second meeting (week 6). The content of the MHE is adopted from the Student Health Service, Department of Health, HKSAR. The MHE is comprised of the following topics:

What is Stress?

[https://www.studenthealth.gov.hk/english/health/health\\_ph/health\\_ph\\_stress.html](https://www.studenthealth.gov.hk/english/health/health_ph/health_ph_stress.html));

Tips on Being Joyful

<https://www.chp.gov.hk/archive/joyful/en/contentsab5e.html?id=40>);

Breathing Exercise practice

[https://www.studenthealth.gov.hk/english/emotional\\_health\\_tips/eh\\_tips/eh\\_tips.html](https://www.studenthealth.gov.hk/english/emotional_health_tips/eh_tips/eh_tips.html));

and

Music listening.

A take home kit which consists of the fact sheet information of the health talk and the video link of the breathing exercise and musical pieces will be provided to the participants after the first meeting. They are instructed to practice the breathing exercise and listening to the musical pieces at home. A weekly reminder via WhatsApp message and email will be sent to the participants to enhance their compliance. In the second meeting, participants will receive the revision talk about on the MHE and share their experience in stress management with the group members.

**Treatment Fidelity.** To ensure treatment fidelity, the certified music therapist will have at least 25 hours of MB programme training; the implementation of the intervention will be supervised by [name], the Co-I. The group sessions will be audio-taped with the consent of the participants, and the recordings will be given to the supervisor for quality monitoring. Written session reports will be provided and regular meetings via Zoom (i.e., three supervisions in the first group, and then two supervisions in the subsequent groups) will be arranged for maintaining the quality of the intervention. The research team will discuss any issues that may arise regarding the study protocol to ensure the quality and consistency of study intervention via regular face-to-face or online meetings.

**Measures.** Primary and secondary measures will be collected at before-intervention (T0), after-intervention (week 6; T1) and 1-month follow-up (week 10, T2) via a self-administered questionnaire. The salivary cortisol levels will be collected at T1.

**Primary outcome**

***Sense of coherence.*** The 13-item Chinese version of the Sense of Coherence Scale (C-SOC-13) (Ding et al., 2012) will be used to measure the comprehensibility, manageability and meaningfulness of the participants' lives (Antonovsky, 1993). This

scale is scored on a 7-point semantic scale with two anchoring phrases, ranging from 1 (very poor) to 7 (very strong). The higher mean score represents a greater sense of coherence. The original SOC-13 was shown to have high internal consistency (Cronbach's  $\alpha = .74 - .91$ ) (Antonovsky, 1993).

### **Secondary outcomes**

***Coping self-efficacy.*** The Coping Self-Efficacy Scale (CSES) is used to measure a person's confidence in their ability to cope effectively with stress (Chesney et al. 2006). It is a 13-item scale with three subscales: (1) use problem-focused coping, (2) stop unpleasant emotions, and (3) seek support from friends and family. The CSES has strong reliability ( $\alpha = 0.79-0.92$ ) and concurrent validity. It is rated on an 11-point scale on which the participant believes they could perform the behaviour. The anchor points range from 0 (cannot do at all), to 10 (certain can do). Higher scores indicate higher levels of coping self-efficacy.

***Emotion regulation.*** The Difficulties in Emotion Regulation Scale (DERS) is used to assess the ability to regulate emotions (Gratz & Roemer, 2004). It contains a total scale score (36 items) and six factors including nonacceptance of emotional response, difficulties in engaging in goal-directed activity, impulse control difficulties, lack of emotional awareness, limited access to emotion regulation strategies, and lack of emotional clarity. Items are measured on a 5-point Likert-type scale from 1 (almost never) to 5 (almost always), with higher values indicating difficulty in emotion regulation.

***Mindfulness.*** The 15-item Mindful Attention Awareness Scale (MAAS) (Chinese version) will be used to assess attentiveness to and awareness of experiences in the present moment (Deng et al., 2012). This scale is scored from 0 (almost always) to 6 (almost never); a higher mean score reflects a higher level of mindfulness. The internal consistency of the scale is good (coefficient of reliability  $> .82$ ).

***Depression, anxiety and stress.*** The 21-item Depression Anxiety Stress Scales (DASS-21) (Chinese version) comprise 21 statements on three components: (a) depression, (b) anxiety and (c) stress (Lovibond & Lovibond, 1995). The scales are scored using a 4-point Likert scale with response options from 0 (does not apply to me at all) to 3 (applies to me very much, or most of the time). The internal consistency has been demonstrated to be good (Cronbach's  $\alpha$  values: Depression = .88, Anxiety = .75, and Stress = .81).

***Subjective general well-being.*** The 24-item BBC Subjective Well-being Scale (BBC-SWB) will be used to measure the participants' subjective experiences of general well-being (Pontin et al., 2013). It measures three components: psychological well-being, physical health and well-being and relationships with good internal consistency (Cronbach's  $\alpha = .94$ ) and concurrent validity ( $r = .640 - .80$ ) (Pontin et al., 2013). The scale is scored using a 5-point Likert-scale.

**Salivary cortisol:** Salivary cortisol levels (sCort) will be used as a biomarker of psychological stress. sCort is considered a reliable measure of hypothalamus pituitary adrenal axis (HPAA) adaptation to stress and correlates well with plasma cortisol (Nater et al., 2013). Average sCort levels in healthy subjects are 5.52 - 28.92 nM/l in the morning; 1.10 - 11.32 nM/l in the afternoon (Bozovic et al., 2013). sCort is stable for several days, non-invasive and easily obtained without adding stress to subjects (Bozovic et al., 2013), and so is suitable for this study in which the participants are required to provide multiple samples at home. Samples will be collected from saliva using Cortisol Salivary Test kits and analysed using a commercially available enzyme-linked immunoassay (eNano Health). Participants will be asked to provide 2 samples: 0700–0800 h and 1600–1700 h to avoid meals within 60 min of providing each sample and to avoid caffeine-containing food and drink during the two days of sampling. Participants will be instructed to keep the samples in an envelope and send to the laboratory for analysis.

**Demographic information.** A self-developed questionnaire will be used to collect demographic information about the participants, including age, gender, educational level, religious beliefs and practices, socioeconomic status and coping behaviour. The latter will be assessed using the Brief Cope Inventory (COPE) (Carver, 1997).

**Statistical analysis.** The statistical analysis will be performed in accordance with the study design, RCT with an intention-to-treat analysis using SPSS, Version 26. The baseline characteristics of the participants in the two arms will be compared to identify any clinically meaningful differences at baseline and at each time point using Chi-square test (for nominal data), Mann-Witney U test (for ordinal or non-normality data) or t-test (for normality data). Any variables considered to be significantly different will be further evaluated (e.g., included as covariates in the statistical analyses) and adjusted to account for their potential confounding effects on the outcomes. To measure both the primary and secondary outcomes, we will obtain repeated measures of multiple outcomes in the two groups, and the data will be analysed using a multivariate approach, such as a MANCOVA or Generalized Estimating Equation (GEE), with adjustment of the baseline outcome variables to test for between-group differences. Correlation analyses will be performed to determine the relationships among the dependent variables. Regression analyses and ANOVA will be conducted to assess significant differences in the effects of the demographic variables on each outcome variable. Repeated measures of ANOVA will be performed to explore the levels of sCort differing within subjects and between groups; between the two sampling days (day) and across the five sampling times (time). Path analyses will be conducted to test the mediating effects between stress-related symptoms and personal strength and emotional regulation. Sub-group analyses will be conducted according to categorisations such as

gender, coping style and religion.

**Ethical considerations.** Ethical clearance will be sought prior to the study from the study institution. Consent will be obtained and anonymity ensured to protect privacy. Participants will receive study information and have autonomy to withdraw from the study at any time.

**Significance of the study.** The call to investigate effective strategies for stress management and improved mental well-being among young people has been prominent in this decade, particularly during the global pandemic period. The findings from the proposed study are expected to provide support for the potential benefits of a therapy option that integrates mindful breathing and music therapy with the intent to engender SOC in coping with stress in young people. The results will add knowledge of SOC to the stress and coping process and support the advancement of stress reduction-related knowledge. The findings will advance the level of professional knowledge, thus supporting researchers, health care professionals and policymakers who plan, implement and evaluate public health services and improve teaching and learning. While the MB programme requires professionally trained music therapists for delivery, the skills can be learned and practised by the participants. This therapy option provides an opportunity for young people to learn the techniques and benefit from the long-term effect of this intervention. In the long run, young people will have improved ability to cope with stressors in their everyday lives and will experience fewer psychological burdens and better health. Furthermore, in an era where the headlines seem dominated by war, plague and global warming, acquiring a coping skill that can be self-practised echoes the social distancing and reduce the demand for healthcare services. For young people, improved mental well-being can facilitate a healthy transition into adulthood and should yield promising results throughout their lives. These individuals are key contributors to the workforce and will contribute to economic growth and a positive societal environment.

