During MB, the level of emotional response can be regulated by intentionally controlling breathing during periods of silence and listening to music. Breathing acts like a ‘volume knob’ to regulate the level of arousal and quality of consciousness. By varying the depth and pace of breathing, one can control arousal from moment to moment. Through breathing, the autonomic functions can be regulated. Based on the above theoretical discussions, we hypothesise that a programme, namely, music breathing (MB), can reduce stress, foster the self-regulation of emotions and facilitate the development of awareness and personal strength, as a result, leading to improved emotional well-being.

Based on the above theoretical discussions, we hypothesise that the MB programme can facilitate the promotion of SOC leading to better coping, reduced stress and better mental well-being. Fig. 1 shows the conceptual framework of the study. In the proposed study, the efficacy of a music breathing programme (MB) will be tested using a randomised controlled trial design. The hypotheses of the proposed study are as follows:

H1: People who receive the MB programme will have better SOC, emotion regulation, coping self-efficacy and mindfulness than those receiving the control condition.

H2: People who receive the MB programme will have reduced stress-related symptoms and better physiological outcome, i.e., salivary cortisol levels than those receiving the control condition.

H3: People who receive the MB programme will have better mental well-being than those receiving the control condition.

H4: There is an association between SOC, coping self-efficacy, emotion regulation and mindfulness.

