**Sample size.** The estimated sample size has been calculated using the statistical package G\*Power 3.1.9.4 (version 2019) for a multivariate analysis of variance (MANOVA) according to the effect size (Cohen's  $d$ ) (between 0.43 and 0.59) of anxiety in previous study on group music-guided imagery (Torres et al., 2018). When converting to a repeated measure (Cohen's  $f$ ), the effect size is considered moderate ( $f = 0.25$ ), with a type I error rate of 5% (2-sided) and assuming a correlation of 0.5 between repeated measures. To achieve 90% power to measure outcome three times in two groups, 232 subjects ( $n=116$  per group) will be required (Cohen, 1988). Assuming a 20% attrition rate (Porter et al., 2012), the trial will require at least 145 participants starting in each arm. We target to complete the recruitment process within 20 weeks; therefore, an average rate of recruitment about 14 subjects per week is anticipated. It might be possible to shorten the recruitment period if the threat posed by the pandemic weakens.

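### H2, H3 and the non-SOC part of H1 rest on secondary outcomes tested with no multiplicity control, decisive time point or exploratory label; if each score is tested at each visit (16 tests at 5%), the chance of a false benefit is about 18–27%

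*Combined protocol and SAP*

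**What the plan says.** - **Hypotheses** (end of The proposed intervention). H1 to H3 are directional between-group claims. H1 covers SOC, emotion regulation, coping self-efficacy and mindfulness. H2 covers stress-related symptoms and salivary cortisol. The third reads "H3: People who receive the MB programme will have better mental well-being than those receiving the control condition".
- **Outcomes.** SOC is the single primary. The secondary outcomes are coping self-efficacy (CSES), emotion regulation (DERS), mindfulness (MAAS), the three DASS-21 scales, subjective well-being (BBC-SWB) and salivary cortisol. Some instruments are described with components; of the DERS the plan says "It contains a total scale score (36 items) and six factors".
- **Timing** (Study design). Questionnaires are completed at T0, T1 and T2. Cortisol has one post-baseline assessment, at T1.
- **Analysis** (Statistical analysis). "To measure both the primary and secondary outcomes, we will obtain repeated measures of multiple outcomes in the two groups", analysed with a multivariate method for which MANCOVA and GEE are given as examples. Cortisol has its own repeated-measures ANOVA, worded as exploration.
- **Error rate.** The only one appears in Sample size: "with a type I error rate of 5% (2-sided) and assuming a correlation of 0.5 between repeated measures".

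The plan does not say how many secondary tests will be run, at which visit, in what order, at what level, or what result would count as support for H1, H2 or H3.

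**The concern.** H2 and H3 contain no primary outcome, and three of the four constructs in H1 are secondary. The numbered hypotheses therefore depend largely on a set of tests with no decision rule. One favourable p-value among many, at either visit, could be reported as support for a hypothesis, and nothing in the plan would prevent it.

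This matters because the Significance section expects the findings to inform professionals and policymakers who plan public health services. A reader who sees a stated 5% error rate would take it to cover the efficacy claims as a set, and it does not.

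**Working it through.** **The plan's own figure.** The plan says "To achieve 90% power to measure outcome three times in two groups, 232 subjects". A global MANOVA test with three responses and two groups has noncentrality f²N = 0.25² × 232 = 14.5 on 3 and 232 − 4 = 228 degrees of freedom. Its power at 5% is 0.902, so 232 reproduces, although this route does not use the stated correlation of 0.5. Attrition: 116 / (1 − 0.20) = 145 per arm. The calculation concerns one test at 5%. It says nothing about the secondary set; 116 per arm is used below only for the cost of the fix.

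**Count if every score is tested at every post-baseline visit.**
- Questionnaire scores: CSES 1 + DERS 1 + MAAS 1 + DASS-21 3 + BBC-SWB 1 = 7.
- At T1 and T2: 7 × 2 = 14.
- Cortisol, morning and afternoon at T1: 2.
- Total: 14 + 2 = 16.

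With one group test per outcome the count is 7 + 2 = 9, or 7 + 1 = 8 with a single cortisol test.

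**Independent tests, no true effect.** The chance of any significant result in either direction is 1 − 0.95^k. A false benefit uses 2.5% per test, giving 1 − 0.975^k.
- k = 16: 56.0% and 33.3%.
- k = 9: 37.0% and 20.4%.
- k = 8: 33.7% and 18.3%.

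The expected number of false positives among 16 tests is 16 × 0.05 = 0.8, of which 0.4 are in the favourable direction.

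**Correlated tests, no true effect.** Multivariate-normal simulation, with three assumptions that the documents do not supply: between-scale correlation 0.3–0.7, T1–T2 correlation 0.5–0.7, and cortisol independent of the scales.

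| Tests | Any significant difference | At least one false benefit |
|---|---|---|
| 16 (each score, each visit) | 35–50% | 18–27% |
| 8–9 (one per outcome) | 22–34% | 11–18% |

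The nominal rates for a single test are 5% and 2.5%.

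**By hypothesis** (independent tests, from the count of 16, taking DASS-21 under H2 and BBC-SWB under H3; the plan does not tabulate this).
- H1 secondary part: 3 scores × 2 visits = 6 tests; 26.5% either direction, 14.1% benefit.
- H2: 3 × 2 + 2 = 8 tests; 33.7% and 18.3%.
- H3: 1 × 2 = 2 tests; 9.8% and 4.9%.

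**Power cost of Holm over eight.** The strictest step uses 0.05 / 8 = 0.00625. With 116 per arm and an assumed baseline–outcome correlation of 0.5, the standardised effect is d / √(1 − 0.5²) = d / √0.75, and the noncentrality is that value × √(116/2).
- d = 0.5: 0.577 × √58 = 4.40; power falls from 99% to 95%.
- d = 0.4: 0.462 × √58 = 3.52; power falls from 94% to 77%.

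**The case against.** The best defence is that the plan names one primary outcome and proposes a multivariate analysis, so secondary results would be read as supportive and an omnibus test would guard against chance findings. If no outcome moves at all, an omnibus MANCOVA used as a gate would hold the error near 5%. That is correct as far as it goes. But the plan leaves the method open and does not say that follow-up tests depend on the omnibus result. Nor can an omnibus test show which of H1, H2 or H3 is supported, and once one outcome truly moves it no longer protects the others. A GEE for each outcome can test both visits jointly, which removes the doubling for T1 and T2 but leaves the multiplicity across outcomes.

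Several stronger readings are tempting, and the documents do not support them:
- **A 35–50% chance of a false benefit.** That range is for a significant difference in either direction. H1 to H3 are directional, so the relevant range for 16 tests is 18–27%.
- **Sixteen as a minimum.** The plan never says that each score is tested separately at T1 and T2; one repeated-measures group test per outcome gives 8–9.
- **About 40 tests, counting subscales.** The CSES, DERS and BBC-SWB components appear only in the instrument descriptions, and no sentence plans to test them.
- **A stated 5% for every secondary test.** The 5% appears only in the sample-size calculation. Its use elsewhere is an inference, though no other level is given.
- **Two confirmatory cortisol tests.** Cortisol has a separate model in exploratory wording. That model also refers to two sampling days and five sampling times, whereas the Salivary cortisol paragraph asks for two samples. The count of two follows the latter.

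**Conclusion.** The gap is real. H2, H3 and the non-SOC part of H1 have no rule that limits false support. How large the inflation is depends on how the open analysis is carried out: about 18–27% for at least one false benefit with 16 tests (33% if independent), or about 11–18% with 8–9 tests. For any significant difference the ranges are 35–50% (56% if independent) and 22–34%.

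These figures assume that each test is run at a two-sided 5%, that there is no true effect, and the correlations given above. The direction of the conclusion does not depend on those correlations: even the lowest benefit figure, 11%, is more than four times the 2.5% for a single test.

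A reader might infer that the trial's main result is compromised. It is not: SOC is a single named primary, and its error rate does not change with the number of secondary tests. The point should be settled before analysis, but it does not bear on the sample size or the conduct of the trial.

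**What to change.** In Statistical analysis, define one secondary family of eight, with one between-group test each:
- CSES total, DERS total and MAAS;
- DASS-21 depression, anxiety and stress;
- BBC-SWB total;
- one cortisol group contrast averaging the morning and afternoon samples at T1, once the plan's two descriptions of cortisol sampling have been reconciled.

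For each questionnaire, state whether the test is at a pre-specified time point or jointly over T1 and T2. T2 need not be barred from claims; what matters is that the choice is fixed in advance. Test the family with Holm at 5%, separately from SOC. State that only Holm-significant results support H1 to H3 on secondary outcomes. Report all subscales and any other single-visit contrasts as estimates with 95% confidence intervals and no claim.

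Labelling every secondary outcome exploratory would also remove the false claims, but H2 and H3 could then no longer be presented as hypotheses that the trial confirms.

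The change is wording only. The cost is lower power per secondary outcome: at the strictest Holm step, 95% instead of 99% at d = 0.5 and 77% instead of 94% at d = 0.4, under the assumptions in the working. The SOC test and the planned 145 per arm stay as they are.
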